#### 9.2.3.4. Cohort 2: Visit 5 and Safety Phone call

Study Visit 5 will be performed in Week 4 of life (Day 22 to 28 of life). The mother will be instructed not to administer the morning DTG dose prior to attending this study visit. Medical staff will take a recent medical history from the parent(s) perform a clinical and laboratory safety visit. Adherence assessment and acceptability testing of DTG will be performed. Study required bloods will be drawn at visit 5, including an HIV NAT test. If any tests yield abnormal results, as specified by protocol specific safety criteria (Section 10), we will consult with paediatricians for appropriate management of the neonate.

Two blood samples will be drawn for PK assessment, one sample immediately prior to administering the morning DTG dose and another sample at 1-3 hrs post-dose (**Table 5**). It is planned to draw 0.4 mL of blood per time point.

The administration of DTG will be stopped by day 28 of life, after which local ARV prophylaxis will be continued as per standard of care.

A telephonic safety visit will be conducted 2 weeks after Visit 5 (+/-4 days). Medical staff will once again take a recent medical history from the parent(s). If no issues are reported, the neonate will exit the study at the conclusion of this visit. If any concerns are noted,

the neonate will be brought back for clinical and special investigations as needed. The total study duration for each individual will depend on the age at enrolment and can range from 5 to 6 weeks.

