**Figure 2** illustrates the procedure for the initial assessment of study eligibility, i.e., the routine PMTCT services identifying HIV-exposed neonates who meet the Stage and Cohort-specific inclusion criteria. The PMTCT nurses will then inform the study team of a potential participant. Postpartum women with HIV receiving DTG-based ART will be allowed to breastfeed or formula feed depending on the mothers' choice. Documentation of maternal HIV-1 RNA result (performed per standard of care) required as part of the inclusion criteria for neonates in Stage 2 will be abstracted from the medical records. If an HIV-exposed neonate is identified as eligible, the parent(s) will be approached to undergo the informed consent process. Following written informed consent from the parent(s) or legal guardian, the participant will be screened for eligibility. A medical history, clinical examination and study required bloods (haematology, chemistry and HIV NAT samples) will be carried out by the study team. If the study required bloods were taken as part of clinical care, results will be documented, and no additional blood draws performed. If the study required bloods (haematology and chemistry) are abnormal (Section 7.2), the neonate will be referred to routine care. Only if the study required bloods (haematology and chemistry) are within the range specified for eligibility will the neonate be allocated to either Cohort 1A, Cohort 1B or Cohort 2 and follow the SOE for that respective Cohort (Section 9.3). Laboratory tests may be repeated during the screening period, with the latest results used to determine exclusion of participant from study enrolment.

**Figure 2:** Summary of procedure for the initial assessment of study eligibility

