### 9.2.3.1. Cohort 2: Screening and Entry visit(s)

The screening and entry visit(s) will take place when the neonate is <7 days of life (Section 9.1). Screening and entry procedures may be performed as one or 2 separate visit(s). At the Entry visit, ZDV prophylaxis will be initiated instead of NVP and continue until DTG is stopped at Day 28 of life. Thereafter, the infant will switch back to NVP from ZDV and continue prophylaxis per national guidelines.

The study team will support the preparation and administration of the 1st dose of the DTG-DT (half-tablet) mixed with water with the parent(s) or caregiver/legal guardian. The exact time of intake will be recorded. The mother will be explained how to prepare and administer DTG at home. Acceptability testing of the DTG-DT will be performed.

Two blood samples will be drawn for PK assessment, one sample immediately prior to administering the 1st DTG dose and another sample at 1-3 hrs post-dose (**Table 5**). It is planned to draw 0.4 mL of blood per time point.

### 9.2.3.2. Cohort 2: Study Visits 2 and Visit 3

It is anticipated that DTG could be dosed every 24, every 48 or every 72 hours, or some other combination, that is expected to achieve target DTG concentrations throughout the first 4 weeks of life. The PK sampling schedule has been designed to cover these different possible dosing scenarios.

After the Entry, Visit 2 can be scheduled at **any time from the 3rd dose of DTG** but before Week 4 of life. The mother will be instructed not to administer the morning DTG dose prior to attending this study visit. On the morning of Visit 2, clinic study nurses and physicians will take a medical history, examine the neonate, and assess adherence. Assessments will include dispensing diary cards to caregivers, reviewing or collecting diary cards and establishing study drug adherence (pill count). The PK assessment should be deferred if the mother/caregiver reports their baby missing any of the previous 3 scheduled doses prior to the PK sampling visit (Section 9.4).

Prior to the morning DTG dose, a blood sample will be taken for pre-dose PK evaluation and then the protocol-specified DTG dose will be administered. The exact time of intake will be recorded. Acceptability testing of the DTG-DT will be performed.

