Physical examination b	X	X		X	
Dispense Study Drug		X			
Acceptability questionnaire		X			
Laboratory					
Haematology c	X (0.5 mL)			X (0.5 mL)	
Chemistry d	X (0.8 mL)			X (0.8 mL)	
HIV-1 NAT Test e	X (0.8 mL)			X (0.8 mL)	
Pharmacology					
PK Blood Sampling f		X (2 mL)	X (0.4 mL)		
Total blood volume	2.1 mL	2 mL	0.4 mL	2.1 mL	

a Screening and entry procedures may be performed as one or 2 separate visit(s). All study required results should be available before entry with the exception of the HIV-1 NAT result which may be pending at time of study entry; b Physical and medical assessment includes length, weight, head measurements and monitoring of vital signs; c Haemoglobin, white blood cell count and differential, and platelets; d Creatinine, ALT, AST, total and direct bilirubin; e If HIV-1 NAT Test comes back positive, the HIV-infected neonate will be taken off study and initiated on standard of care HIV-treatment, as per local guidelines; f PK blood sampling will occur at the following time points: pre-dose and 1, 2, 4, 6 and 24-72 hours post dose. Mothers and their neonates will return home after PK Visit 1a and attend 24–72 hours later (as applicable) for PK Visit 1b. Laboratory tests may be repeated during the screening period dependent on specified blood draw limits.

**Table 8.** Schedule of evaluations for Stage 2 Cohort 2 (n=24): Multiple doses of DTG in neonates commencing within 72 hours of life

Evaluation	Screening and Entry Visit(s) a	Visit 2	Visit 3	Visit 4	Visit 5	Safety Phone Call
Visit windows	< 7 days of life	Any time from 3 rd DTG dose but before Week 4 of life b	24 to 72 hours post Visit 2 DTG dose	1 week after Visit 2 (+/- 4 days) c	Week 4 of life (Day 22 – 28 of life)	2 weeks after Visit 5 (+/-4 days)
Clinical						
Informed Consent	X					
History	X	X	X	X	X	X
Physical examination d	X	X		X	X	
Dispense Study Drug e	X	X	X	X	X	
Acceptability questionnaire	X	X		X	X	
Adherence assessments		X		X	X	
Laboratory						
Haematology f	X (0.5 mL)			X (0.5 mL)		
Chemistry g	X (0.8 mL)	X (0.8 mL)		X (0.8 mL)	X (0.8mL)	
HIV-1 NAT Test f	X (0.8 mL)				X (0.8 mL)	
Pharmacology						
PK Sampling i	X (0.8 mL)	X (2.0 mL)	X (0.4 mL)		X (0.8mL)	

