Total blood volume	2.9 mL	2.8 mL	0.4 mL	1.3 mL	2.4 mL	

a Screening and entry procedures may be performed as one or 2 separate visit(s). All study required results should be available before entry with the exception of the HIV-1 NAT result which may be pending at time of study entry; b Visit 2 and 3 should be scheduled any time from 3rd DTG dose but before week 4 of life; c Visit 4 can be conducted on the same day as Visit 5 but only if both falls within week 4 of life; d Physical and medical assessment includes length, weight, head measurements and monitoring of vital signs vital signs; e 1st DTG dose administered <7 days. The timing of the next dose of DTG and subsequent DTG doses will be determined using data from Cohort 1A and 1B. DTG will be administered until the neonate is 28 days old; f Haemoglobin, white blood cell count and differential, and platelets; g Creatinine, ALT, AST, total and direct bilirubin; h If HIV-1 NAT Test comes back positive, the HIV-infected neonate will be taken off study and initiated on standard of care HIV-treatment, as per local guidelines; i For the 1st DTG dose (PK: pre-dose sample and 1 more sample 1-3 hours post-dose); Any time from 3rd DTG dose but before week 4 of life (PK: pre-dose and 1, 2, 4, 6 and 24-72 hours post dose); For any DTG dose in Week 4 of life (PK: pre-dose sample and another sample 1-3 hours post-dose). Laboratory tests **may not** be repeated during the screening period as this will exceed blood draw limits.

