### **13.7. Blood Draw Limitations**

The maximum amount of blood that may be drawn from a neonate for clinical and research purposes in one blood draw shall not exceed 5, 6 or 8 mL for a 2, 3 or 4 kg neonate, respectively (2.5% of the total blood volume), neither will the blood drawn in a 30-day period exceed 10, 12 or 16 mL for a 2, 3 or 4 kg neonate. This is in alignment with the SU HREC guideline for paediatric blood volumes for research purposes (57). Based on studies performed by our institution, the blood volumes required for this study have been feasible and acceptable.

Bloods drawn during the study period will be done for safety purposes, HIV diagnosis and PK assessments. There will be no long-term storage of any blood samples and no genetic testing will be performed.

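### Cohort 2: the text calls for study bloods at Visit 5, but Table 8 has no haematology there, so the last scheduled blood count can fall well before treatment ends on day 28

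*Protocol*

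**What the plan says.** Protocol section 9.2.3.4 makes Visit 5 (day 22 to 28 of life) a safety visit with both clinical and laboratory assessment, and states: "Study required bloods will be drawn at visit 5, including an HIV NAT test". After it there is only a telephone contact two weeks later.

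Section 9.1 explains the term for screening: "study required bloods (haematology, chemistry and HIV NAT samples) will be carried out by the study team". It spells the term out twice more in the same section, both times as haematology and chemistry without the NAT.

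Table 8 (section 9.3) marks haematology, 0.5 mL, at Screening/Entry and at Visit 4 only. Chemistry is marked at entry and at Visits 2, 4 and 5. Table 8 places Visit 4 "1 week after Visit 2 (+/- 4 days"), whereas section 9.2.3.3 makes a week the minimum and still attaches the 4-day tolerance. Of the full PK visits, a Table 8 footnote says "Visit 2 and 3 should be scheduled any time from" the third DTG dose, but before week 4. Visits 4 and 5 may share a day if both fall in week 4.

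On the background drug, section 9.2.3.1 says: "At the Entry visit, ZDV prophylaxis will be initiated instead of NVP and continue until DTG is stopped at Day 28 of life". On blood volume, section 13.7 says "neither will the blood drawn in a 30-day period exceed 10, 12 or 16 mL for a 2, 3 or 4 kg neonate".

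**The concern.** The text and the schedule give a site two different instructions for Visit 5. A site that follows Table 8 takes one on-treatment count per infant, at Visit 4. Visit 4 is tied to Visit 2, and Visit 2 can come as early as the third dose, so that count may fall in the first or second week of life.

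This bears on a primary endpoint. Section 5.3.1 counts participants with adverse events of Grade 3 or higher. Section 10.1 makes a new or worsened haematology result an adverse event, and section 10.2 makes any Grade 3 or higher event serious. Related Grade 3 or higher events also feed the Cohort 2 hold rule in section 11.1.3. A laboratory abnormality without symptoms can enter these counts only if blood is drawn.

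The schedule also sits oddly with exposure. Cohorts 1A and 1B receive one dose and have haematology about a week later, after all their dosing. Cohort 2 receives repeated DTG with protocol-assigned ZDV to day 28, and may have its last count with much of that exposure still to come.

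**Working it through.** **1. Is the empty Visit 5 cell real?** The Table 8 volumes (mL) were summed by visit and compared with the printed totals.

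| Visit | Haematology | Chemistry | NAT | PK | Sum | Printed |
|---|---|---|---|---|---|---|
| Entry | 0.5 | 0.8 | 0.8 | 0.8 | 2.9 | 2.9 |
| 2 | – | 0.8 | – | 2.0 | 2.8 | 2.8 |
| 3 | – | – | – | 0.4 | 0.4 | 0.4 |
| 4 | 0.5 | 0.8 | – | – | 1.3 | 1.3 |
| 5 | – | 0.8 | 0.8 | 0.8 | 2.4 | 2.4 |

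All five totals reproduce. The Visit 5 total leaves no volume for haematology, so the empty cell is in the plan and is not a fault of text extraction.

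**2. How long can the gap be?** Gap = 28 − (day of first dose + 2 × dosing interval + days from Visit 2 to Visit 4). The third dose comes two intervals after the first. Intervals of 1, 2 and 3 days are those in Table 4.

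| First dose | Interval | Earliest Visit 2 | Gap, Visit 4 at +7 days | Gap, Visit 4 at +3 days |
|---|---|---|---|---|
| Day 1 | Q24h | Day 3 | 28 − 10 = 18 | 28 − 6 = 22 |
| Day 1 | Q48h | Day 5 | 28 − 12 = 16 | 28 − 8 = 20 |
| Day 1 | Q72h | Day 7 | 28 − 14 = 14 | 28 − 10 = 18 |
| Day 6 | Q24h | Day 8 | 28 − 15 = 13 | 28 − 11 = 17 |
| Day 6 | Q48h | Day 10 | 28 − 17 = 11 | 28 − 13 = 15 |
| Day 6 | Q72h | Day 12 | 28 − 19 = 9 | 28 − 15 = 13 |

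The +3 column uses the early edge of the Table 8 window (7 − 4). The +7 column is both the nominal Table 8 timing and the minimum if section 9.2.3.3 is read strictly. The day of birth is counted as day 1; counting it as day 0 would add one day to the maximum.

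The gap can also be short. If Visits 4 and 5 coincide on day 22 to 28, it is 28 − 28 = 0 to 28 − 22 = 6 days. If Visit 2 is as late as day 21, Visit 4 at +7 falls on day 28 and there is no gap.

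**3. Does an added sample fit?** The scheduled total is 2.9 + 2.8 + 0.4 + 1.3 + 2.4 = 9.8 mL. With 0.5 mL more at Visit 5 it is 10.3 mL. Entry to Visit 5 lies within 28 days of life, so the 30-day limit covers the whole sum: 10.3 mL exceeds 10 mL at 2 kg and is within 12 mL at 3 kg and 16 mL at 4 kg. The Visit 5 draw becomes 2.4 + 0.5 = 2.9 mL, against 5 mL per draw at 2 kg.

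Section 13.7 gives no limit between 2 and 3 kg. If it is interpolated linearly (an assumption), 10 + 2 × (weight − 2) = 10.3 at 2.15 kg. If the 2 kg limit holds until 3 kg, the extra sample fits only from 3 kg.

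**The case against.** The best defence is that the term is used loosely and the table governs. The three-part list in section 9.1 describes screening. The other two uses there omit the NAT, sections 9.2.1.2 and 9.2.2.2 name the NAT separately, and section 9.2.3.3 uses the term for Visit 4, where Table 8 has no NAT. Section 9.1 also tells allocated infants to follow the schedule of evaluations. On that view the term means whatever Table 8 lists. This weakens the idea of a protocol-wide definition, but no spelled-out use leaves haematology out, so the two instructions still conflict.

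A second defence is that the omission is a deliberate trade-off. The plan stands at 9.8 mL against 10 mL at 2 kg, section 9.2.3.5 says sampling was designed around the limit, and chemistry, which covers the bilirubin, liver and creatinine concerns that the protocol names, is taken at Visit 5. A mid-course count has the merit that drug can still be held. This may well be the reason, but the protocol does not give it for haematology, and section 9.2.3.4 reads otherwise.

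Third, 22 days is a corner case. It needs a first dose on day 1, Q24h dosing from the start, Visit 2 exactly at the third dose and Visit 4 four days early. Sections 8.2.1 and 9.2.3 expect longer intervals in early life. That stands, and 22 days should be read only as a maximum.

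Fourth, a reader might infer that any late cytopenia would go uncounted. The documents do not support that. Visit 5 has a history and examination, the later call can bring the infant back for investigation, and adverse events are collected to study end. Only events detectable by laboratory test alone would be missed. Nor do the documents name a haematological risk of DTG or of its combination with ZDV.

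**Conclusion.** The mismatch is real and should be resolved before sites work from it. Section 9.2.3.4, read with section 9.1, calls for haematology at Visit 5; Table 8 does not schedule it. Under Table 8, the last count precedes day 28 by 14 to 18 days for a first dose on day 1 and Visit 4 a week after the earliest Visit 2. The figure is 9 to 13 days for a first dose on day 6, at most 22 days in the extreme case, and 0 to 6 days when Visits 4 and 5 coincide. These are scheduled counts; unscheduled clinical tests could shorten the gap.

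The consequence is limited to asymptomatic, laboratory-only Grade 3 or higher haematological events late in treatment, which would be missing from the primary safety endpoint in the multi-dose cohort. A reader might go further and conclude that the Visit 4 sample should be moved to Visit 5 for the smallest infants, which keeps 9.8 mL. The documents do not settle that. It would give up the mid-treatment count and leave no scheduled count between entry and day 22 to 28, so it is a trade-off for the sponsor to decide and state.

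**What to change.** - Reconcile sections 9.1, 9.2.3.3, 9.2.3.4 and Table 8: define once what the study required bloods are at each visit, and give one Visit 4 window.
- Add the 0.5 mL haematology sample to the existing Visit 5 draw for infants whose section 13.7 30-day limit permits it, and state how the limit applies between 2 and 3 kg. Where Visits 4 and 5 coincide, the Visit 4 sample already serves and nothing need be added.
- For infants near 2 kg, where both samples do not fit, state which visit carries the single on-treatment count and why.
- In the safety report, give age and days of exposure at the last count for each Cohort 2 infant, so that readers can see how much exposure the haematology covers.

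The cost is an amendment to the schedule and text, with no new visit. The extra 0.5 mL brings the total to 10.3 mL and leaves less room for the confirmatory tests in section 10.8 and rescheduled PK sampling in section 9.4. Correcting only the text to match Table 8 would remove the contradiction without extra blood, but would leave the late-treatment gap in place.

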	
All infants in Stage 2 will be followed for safety until 2 weeks after the last PK visit. An interim PK and safety analysis will be performed after 50% of participants have completed Cohort 2 to assess if a dose adjustment is required and to review safety data. Following the DSMB interim review, a different DTG dosing schedule may be selected based on the data available for the remainder of Cohort 2 infants. Any change to the DTG dosing schedule will be agreed upon by the DSMB before implementation.

Inclusion criteria
	
Written informed consent to participate in the study must be obtained for all participants from the parent(s) or legal guardian.
 
Stage 1
 
 
• HIV-exposed term neonate (pending HIV status) born to a woman within HIV on DTG-based ART
 
• Birth weight of <math>\geq 2000</math> g and on standard of care ARV prophylaxis
 
 
Cohort Specific Inclusion Criteria must be met at Study Entry:
 
Cohort 1A: Infant <14 days of life  Cohort 1B: Infant <math>\leq 3</math> days of life
 
Stage 2
 
 
• Low risk* HIV-exposed term neonate (pending HIV status) born to a virologically suppressed woman on DTG-based ART  *Neonate born to a woman with a documented plasma HIV-1 RNA result <50 copies/mL in the 4 weeks prior to delivery or between delivery and infant study entry
 
• Birth weight of <math>\geq 2000</math> g and on standard of care ARV prophylaxis
 
 
Cohort Specific Inclusion Criteria must be met at Study Entry:
 
Cohort 2: Infant <7 days of life

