### 9.2.2.2. Cohort 1B: Safety Visits

One week after PK Visit 1a (+/-4 days), we will conduct a clinical and laboratory safety visit. Medical staff will take a recent medical history from the parent(s) and examine the neonate. Study required bloods will be drawn, and an HIV NAT will be performed. If any tests yield abnormal results, as specified by protocol specific safety criteria (Section 10), we will consult with paediatricians for appropriate management of the neonate. If all tests are normal, a telephonic safety visit will be conducted 2 weeks after PK Visit 1a (+/-4 days). Medical staff will once again take a recent medical history from the parent(s). If no issues are reported, the neonate will exit the study at the conclusion of this visit. If any concerns are noted, the neonate will be brought back for clinical and special investigations as needed. The total study duration for each individual will depend on the age at enrolment and can range from 3 to 4 weeks.

If study safety hold criteria (Section 11.1.2) are met at any time during Cohort 1B the study will be paused, safety data reviewed, and a DSMB meeting held to determine if the study should continue (Section 6.2, **Figure 1**). After Cohort 1B is complete, all safety and PK data for Stage 1 will be reviewed. Pharmacokinetic modelling and simulation analyses using Stage 1 PK data will be performed to select the multi-dose schedule of 5 mg DTG for Cohort 2. All findings will be presented to the DSMB before opening Cohort 2 (Section 11.4).

### 9.2.3. Stage 2: Cohort 2

Low-risk HIV-exposed neonates in Cohort 2 will receive multiple 5 mg doses of DTG.

DTG administration will begin within 7 days of life and continue until day 28 of life on top of ARV postnatal prophylaxis. Due to the potential drug-drug interaction between NVP and DTG, the low-risk neonates enrolled in Stage 2 will receive ZDV prophylaxis, instead of NVP, for the duration of the study (Section 8.2.1 and Section 13.6).

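### Cohort 2's exit safety call is timed from Visit 5, not the last dose, so follow-up after a day-28 dose is 8 to 14 days on schedule (4 to 18 with the window)

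*Protocol*

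**What the plan says.** The end of follow-up in Cohort 2 is set in Section 9.2.3.4: "A telephonic safety visit will be conducted 2 weeks after Visit 5 (+/-4 days"). The next step is exit: "If no issues are reported, the neonate will exit the study at the conclusion of this visit". Table 8 gives the same window. The synopsis puts the rule in terms of sampling: "All infants in Stage 2 will be followed for safety until 2 weeks after the last PK visit". The last PK visit is Visit 5, so these three places agree with each other.

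Visit 5 itself has a seven-day range: "Study Visit 5 will be performed in Week 4 of life (Day 22 to 28 of life"). Table 5 lets its PK dose be any week-4 dose, so it need not be the last one.

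Dosing is tied to age, not to Visit 5. Section 9.2.3 says "DTG administration will begin within 7 days of life and continue until day 28 of life", and footnote e of Table 8 says "DTG will be administered until the neonate is 28 days old". Section 9.2.3.4 words it slightly differently: "The administration of DTG will be stopped by day 28 of life".

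Section 9.2.3.4 also states that each infant's total time on study depends on age at enrolment and "can range from 5 to 6 weeks".

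**The concern.** In Stage 1 the only dose is given at PK Visit 1a. A call timed from that visit is therefore also timed from the last exposure. Cohort 2 carries the wording over, but there the visit and the last dose can be up to six days apart. The interval between the end of treatment and study exit then depends on an appointment date.

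Safety is a primary objective. Section 10.3 collects adverse events from consent until the study ends, and Section 12.2.3 summarises them as simple proportions of participants. If observation after treatment differs between infants for scheduling reasons, those proportions rest on unequal time at risk. The events most affected are those that begin after the last dose. Cohort 2 is the multi-dose cohort, so this is where a uniform post-exposure period is most useful.

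**Working it through.** **Inputs**
- Visit 5: day 22 to 28 of life (Section 9.2.3.4, Table 8).
- Call: Visit 5 + 14 days, +/-4 days, so 10 to 18 days after Visit 5.
- Entry: before 7 days of life (Section 9.2.3.1), taken as day 0 to day 6.
- Last dose: day 28 (Section 9.2.3, Table 8 footnote e).
- Possible dosing intervals: 24, 48 or 72 hours (Table 4).

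**1. The protocol's own figure: 5 to 6 weeks on study**

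Duration = exit day - entry day.

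| Call timed from | Shortest | Longest |
|---|---|---|
| Visit 5, on schedule | 22+14-6 = 30 days (4.3 weeks) | 28+14-0 = 42 days (6.0 weeks) |
| Visit 5, with window | 22+10-6 = 26 days (3.7 weeks) | 28+18-0 = 46 days (6.6 weeks) |
| Day 28, on schedule | 28+14-6 = 36 days (5.1 weeks) | 28+14-0 = 42 days (6.0 weeks) |
| Day 28, with window | 28+10-6 = 32 days (4.6 weeks) | 28+18-0 = 46 days (6.6 weeks) |

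The 5-week lower end is not reproduced from Visit 5. It is reproduced, nominally, from day 28. Counting entry from day 1 lowers only the longest figures by one day.

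**2. Follow-up after a day-28 last dose**

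Gap = Visit 5 day + offset - 28.

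| Visit 5 | Call at +10 | Call at +14 | Call at +18 |
|---|---|---|---|
| Day 22 | 4 | 8 | 12 |
| Day 24 | 6 | 10 | 14 |
| Day 26 | 8 | 12 | 16 |
| Day 28 | 10 | 14 | 18 |

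On schedule the range is 8 to 14 days. If Visit 5 is assumed to be spread evenly over days 22 to 28, the mean is 11 days. With the window the range is 4 to 18 days. In Stage 1 the same rule gives 14 days after the dose, or 10 to 18 with the window.

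**3. Does the dosing interval rule out the shortest gap?**

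No. An infant dosed at Visit 5 on day 22 has 28-22 = 6 days left, which is divisible by 1, 2 and 3. A day-28 dose is therefore reached at 24-, 48- and 72-hour intervals alike. If the last dose must instead fall before day 28, the smallest gap becomes 5, 6 or 7 days respectively.

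**4. Drug remaining at the call**

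Fraction remaining = 2^(-hours/half-life). Four days is 96 hours.
- Half-life 32.8 h (Section 8.2.1, washout after in utero exposure): 2^(-96/32.8) = 13%.
- Half-life 14 h (Section 8.1, general value after oral intake): 2^(-96/14) = 0.9%.

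The protocol gives no half-life for infants of 28 to 32 days, so the residue at day 4 is best stated as a range of about 1% to 13%. The unequal follow-up in step 2 does not depend on this figure.

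**The case against.** Most of the case against making more of this stands.

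- **A reader might infer that Cohort 2 is promised two weeks after the last dose.** It is not. The synopsis, Section 9.2.3.4 and Table 8 consistently use Visit 5 or the last PK visit. The two-week benchmark comes from how the rule works in Stage 1 and from the stated duration. This is a poorly chosen anchor, not a contradiction between rules.
- **A reader might take 4 days as the usual gap.** It needs Visit 5 on day 22, the call on its earliest permitted day, a last dose on day 28 and no reported concern. The window also works the other way: Visit 5 on day 24 with a call at +18 gives a full 14 days.
- **A reader might infer that clinical events in the last week of dosing go unrecorded.** The earliest possible call is day 32, after dosing has ended. Staff take a recent history at that call and bring the infant back if there is a concern. Section 10.3 follows serious events to resolution or a stable state.
- **A silent laboratory change after Visit 5 could be missed**, since Table 8 schedules no blood test after that visit. Moving the call would not detect it either.
- **Cohort 2 is not under-observed overall.** Even in the shortest case, with entry and first dose on day 6, it is followed for 26 days from the first dose, against 10 to 18 in Stage 1. It also has more scheduled chemistry.
- **The 13% residue is probably an upper bound.** It uses a half-life from washout at birth, and Section 10.7.1 describes UGT1A1 activity as rising rapidly in the first months of life.

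What remains is that post-treatment observation varies with a booking date, and that the stated duration does not follow from the written schedule.

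**Conclusion.** The point holds as a minor one. The Visit 5 anchor gives 8 to 14 days of follow-up after a day-28 last dose on schedule, and 4 to 18 days with the window. The stated 5 to 6 weeks agrees with a call timed from day 28, but not with one timed from Visit 5, where the nominal range is 4.3 to 6.0 weeks.

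The day counts assume that dosing reaches day 28, as Section 9.2.3 and Table 8 state, and that entry is between day 0 and day 6. The consequence is limited to unequal coverage of adverse events that arise after the last dose. No PK endpoint, dose-selection criterion or safety hold rule is affected. The documents support neither a broken promise of two weeks after treatment nor a general loss of events from the last dosing week.

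**What to change.** In the synopsis, Section 9.2.3.4 and Table 8, time the telephone safety call 2 weeks (+/-4 days) after the later of Visit 5 and the last dolutegravir dose taken. For a day-28 last dose the call is then due on day 42 (day 38 to 46), which gives 14 days (10 to 18) after treatment, as in Stage 1. The stated 5 to 6 weeks then holds nominally and needs no change.

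The wording on the end of dosing (until, at or by day 28) should be reconciled at the same time, so that the anchor is unambiguous. Doses after Visit 5 are taken at home, so the call can be booked from the planned last-dose date and the actual date confirmed during the call.

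The cost is a short amendment. The call's target date moves by at most 6 days (42-36, for a day-22 Visit 5), and the latest possible exit stays at day 46. No visit, blood draw or treatment change is added.
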